If subjects initiated at Visit 3 on the 20 mg dose report symptoms as described above, the same process will be followed; however, the physician may have to withdraw the subject since a dose lower than 20 mg tid is not an option.

Methemoglobin. If subjects report change in skin tone and dizziness or other signs of methemoglobinemia for ≥ 24 hours, an interim visit will be requested. Methemoglobin will be assessed. If greater than 5%, a nitrite dose reduction is proposed from 40 mg three times daily to 20 mg three times daily. Subjects will be contacted via phone for the next 2 days for symptom re-assessment. If symptoms remain resolved, subjects will continue on 20 mg tid. If symptoms persist, subjects will be requested to come in for repeat methemoglobin testing after 3 days. If level persists above 5%, participation in the study for the subject will be discontinued.

Safety of holding anti-platelet or antithrombotic medications

The research physician and the staff under his auspice will guide holding of the antiplatelet and anti-thrombotic medications. In each case, this will be discussed doctor to doctor by the research doctor and the patient's PCP or cardiologist.

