Subjects will rest for approximately 30 minutes post biopsy while wound is dressed and prior to baseline vitals prior to dosing. Study staff will record a baseline level of symptoms, including shortness of breath, dizziness, lightheadedness for use during weekly phone calls, prior to dosing.

Following biopsy, subjects will receive their first dose of study drug as follows:

- 14N sodium nitrite, 20 or 40 mg per physician order
- Blood pressure (sitting and then standing after 3 minutes), HR, RR, pulse oximeter and methemoglobin will be measured to ensure they are at a steady state before taking the study drug (baseline) and then approximately every 15 minutes for the 2 hours post-drug administration. Any perturbations of concern will be addressed per the Dose Reduction protocol described in Section 2.2.6.
- AE assessment
- Provide a 42-day supply of study drug, pre-filled in 4 weekly pill boxes and an extra bottle and drug diary cards to assist with compliance and reduce burden or confusion. Study staff will review medication administration and use of the drug diary card with all subjects. Study staff or CTCR RN will review biopsy site care with subjects and if indicated, remind subjects to resume their normal anti-coagulation and anti-platelet medications the following day (as indicated).
- 24-hour dietary recall. The study coordinator will collect a second 24-recall of all foods eaten from subjects for analysis for calories, macronutrients, sodium, nitrates and nitrites.

Subjects will be reminded before departure to report promptly any changes in their medication, health or symptoms of concern, not to wait for the weekly call.

Visit 4 (First Completion Assessment visit to be scheduled 25-35±7 days following first dosing of 20-40 mg oral nitrite) Subjects who need more than 42 days' supply of drug due to scheduling later in window will be issued additional at visit 3.

This visit will take place in the EMRC and/or Pepper SMART Center and is identical to visit 2 (approximately 3 hours):

Interval history and brief physical exam: temperature, blood pressure, pulse oximetry for methemoglobin %, breathing rate, heart rate and body weight; additionally, AE and symptom assessment will be collected and medication compliance via drug diary cards and pill boxes will be assessed.

Physical Function Battery:

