5. POTENTIAL RISKS AND BENEFITS

5.1 POTENTIAL RISKS

5.1.1 Risk of Experimental Drug Intervention

Numerous studies have evaluated acute, subacute and chronic drinking water exposures of nitrate and nitrite in laboratory animals and drinking water and dietary exposures in humans. Recent studies are available using high doses of nitrite by oral route in the form of beet root juice. Recent studies have evaluated acute exposures of oral preparations of nitrite and nitrate on PK and blood pressure and are characterized below. More extensive human data is available on parenteral sodium nitrite as it is currently available and approved by the FDA for use in the

emergency treatment of cyanide poisoning^{31,32}. It is also notable that neutrapharmaceutical preparations are currently being sold with levels of nitrite (12.7 mg per tablet) and nitrate (3.9 mg per tablet).

Nitrite:

Sodium nitrite has been used commercially as a food preservative, an anti-corrosive agent, a coloring agent, and an anti-anginal agent, with additional uses in laxatives, burn ointments, and liniments. Amyl nitrite has been inhaled or ingested as an euphoric stimulant. Nitrite has also been found as a contaminant in well water. Literature searches generated case reports of nausea, vomiting, abdominal pain, dizziness, headache, flushing, cyanosis, tachypnea, dyspnea, hypotension and death attributed to excess nitrite (high-dose) exposure from these sources as a consequence of methemoglobinemia due to oxidation of heme-iron in oxyhemoglobin. Normal background methemoglobin production is 1-3%. If levels of methemoglobin rise above approximately 30% of total hemoglobin, a subject may appear cyanotic and experience dyspnea, due to the reduced oxygen carrying capacity of hemoglobin (methemoglobin cannot bind oxygen). Levels above 50% can cause seizures, hypotension, coma and death. Sodium nitrite administration for cyanide poisoning at the labeled dosage of 300 mg causes methemoglobinemia, a desirable effect, as methemoglobin binds to cyanide, thus protecting cellular mitochondria. A standard dose of nitrite used for cyanide poisoning is 300 mg up to 600 mg. Note that methemoglobin levels have never risen higher than 3% at the currently used therapeutic doses (<75 mg) in 80 volunteers in phase I studies at the NIH.

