A recent study determined the safety and feasibility of prolonged intravenous nitrite infusion. Twelve adult volunteers received increasing starting doses of sodium nitrite, 4.2 to 533.8 µg/kg/hr for 48 hours. Dose limiting toxicity occurred at 445.7 µg/kg/hr (10.6 mg/kg/day) and was limited to asymptomatic transient decreases of arterial blood pressure of up to 20 mmHg and asymptomatic increases of methemoglobin levels above 5%. No tolerance or clinically significant rebound was observed³⁶. Note this is 8.2 times the daily dose we plan to use in this trial (based on an adult body weight of 95 kg).

For nitrite, two retrospective case-control studies have shown that high maternal dietary nitrite intake from cured meat or drinking water during pregnancy might be associated with risk of childhood brain tumors and possibly gastric and esophageal cancer. This evidence is only based on retrospective case-control studies; cohort studies have found no significantly increased risks²⁴.

In the 2001 National Toxicology Program (NTP) Report summarizing 2-year rodent drinking water studies, there was no evidence of carcinogenic activity of sodium nitrite in male or female F344/N rats exposed to up to 130 mg/kg/day in males and 150 mg/kg/day in females, or in male B6C3F1 mice exposed to up to 220 mg/kg/day. There was equivocal evidence of carcinogenic activity of sodium nitrite in the highest dose of 165 mg/kg/day in female B6C3F1 mice based on the positive trend in the incidences of squamous cell papilloma or carcinoma (combined) of the forestomach. Exposure to sodium nitrite in drinking water resulted in increased incidences of epithelial hyperplasia in the forestomach. However, no chromosomal damage (genetic toxicity) was observed in three studies conducted in rats and mice *in vivo*³⁷. Taken together, these findings suggest minimal carcinogenic nitrite-mediated risk.

In the current study, we will use much lower doses of nitrite than used safely in any of these studies. Our nitrite dose of 20-40 mg three times daily is lower than the dose used on the cardiovascular IND and <40% of the dose for cyanide poisoning.

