Any event meeting #1 or #2 above will be reported immediately to the IRB in their required format. In the event that a participant either withdraws from the study or the PIs decide to discontinue a participant due to a SAE, the participant will be monitored by the co-PIs until (a) a resolution is reached (e.g., the problem has resolved or stabilized with no further change expected), (b) the SAE is determined to be clearly unrelated to the study intervention, or (c) the SAE results in death. Outcomes of SAEs will be regularly reported to the IRB. A summary of the SAEs that occurred during the previous year will be included in the annual progress report as well as in the annual IRB renewal. Suicidal ideation and AEs will be formally assessed immediately after treatment and referrals for further care will be made as needed. In the Informed Consent Form, we will provide specific information about emergency contacts. Participants are instructed to contact [name] during working hours. After hours participants will be provided the information on how to contact the cardiology fellow on call.

Stopping Rule:

For safety reasons, we propose to discontinue participation for any subject who experiences *any of the following*:

1. Methemoglobin greater than 5% after dose lowering
A nitrite dose reduction is proposed from 40 mg three times daily to 20 mg three times daily if this methemoglobin % is reached at any study interim visit, as described in section 2.2.6 (phone report of change in skin tone and dizziness or other symptom suggestive of methemoglobinemia). Follow up symptom assessment for 48 hours and repeat methemoglobin in 3 days will be implemented. If methemoglobin is greater than 5% on the lower nitrite dose, participation in the study for the subject will be discontinued.
2. Blood pressure drop after dose lowering
Blood pressure and related symptoms.

If subjects experience lightheadedness or dizziness after visit 3 while they are on the drug, we request that they call the study coordinator who will inventory their symptoms, compare to baseline (measured at pK) levels, and discuss need for interim visit with study physician. If a visit is indicated, we will measure blood pressure, RR, heart rate, and check methemoglobin level by a finger probe. A study physician will evaluate each subject, including:

- a. review of all clinical measures,
- b. subject history of symptoms,

c. blood pressures pre- and while on drug.

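### After a dose cut for methemoglobin above 5%, section 2.2.6 repeats the test only if symptoms persist, while stopping rule item 1 in section 5.4.1 requires the 3-day repeat in everyone reduced

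*Combined protocol and SAP*

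**What the plan says.** Two places in the combined protocol and SAP govern what happens after methemoglobin above 5% in a subject on 40 mg three times daily.

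- **Section 2.2.6 (Dose reduction, methemoglobin paragraph).** Symptoms lasting 24 hours or more lead to an interim visit. A level above 5% leads to a cut to 20 mg three times daily, with phone calls about symptoms over the next 2 days. The text then branches. For the subject who feels better: "If symptoms remain resolved, subjects will continue on 20 mg tid". For the subject who does not: "If symptoms persist, subjects will be requested to come in for repeat methemoglobin testing after 3 days". If that repeat is still above 5%, the subject is discontinued.
- **Section 5.4.1 (Stopping Rule, item 1).** The same reduction applies "if this methemoglobin % is reached at any study interim visit, as described in section 2.2.6". What follows has no branch: "Follow up symptom assessment for 48 hours and repeat methemoglobin in 3 days will be implemented". The rule ends: "If methemoglobin is greater than 5% on the lower nitrite dose, participation in the study for the subject will be discontinued".

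Methemoglobin is also read at scheduled visits. Table 1 marks it at Visits 3, 4 and 5, and the Visit 4 text in section 2.3.1 lists "pulse oximetry for methemoglobin %, breathing rate, heart rate and body weight; additionally, AE and symptom assessment will be collected".

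**The concern.** The stopping criterion in section 5.4.1 is a measured level after dose lowering, so it can be judged only if the level is measured again. Section 5.4.1 guarantees that measurement at 3 days. Section 2.2.6, which section 5.4.1 cites as the source of the procedure, guarantees it only for subjects who still have symptoms.

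Relief of symptoms is a weak substitute for the reading. Section 5.1.1 says "If levels of methemoglobin rise above approximately 30% of total hemoglobin, a subject may appear cyanotic and experience dyspnea", so a subject could be free of those signs and still be above 5%. Staff working from section 2.2.6 would leave such a subject on 20 mg three times daily without confirming that a level known to have exceeded the protocol's own limit has come down. Staff working from section 5.4.1 would check. The stake is the safety of individual subjects and consistent use of a stopping rule.

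**Working it through.** No statistical figure is involved. The check sets the two rules side by side and then works out how long the next required reading could be delayed.

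**Comparison**

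| Step | Section 2.2.6 | Section 5.4.1, item 1 |
|---|---|---|
| Trigger | Reported symptoms, interim visit, level above 5% | Same, by reference to 2.2.6 |
| Action | 40 mg to 20 mg three times daily | Same |
| Symptom follow-up | Phone, 2 days | 48 hours |
| Repeat test, symptoms persist | At 3 days | At 3 days |
| Repeat test, symptoms gone | None stated | At 3 days |
| Above 5% on lower dose | Discontinue (if retested) | Discontinue |

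The rules differ in one cell only: the repeat test in a subject whose symptoms have gone.

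**Delay to the next required reading**

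Inputs: the repeat interval is 3 days (sections 2.2.6 and 5.4.1). Visit 4 falls on day 25 to 35 (section 2.3.1 and Table 1), with a further window of 7 days either side. Phone calls fall on about days 7, 14, 21 and 28 (Table 1), and no methemoglobin reading is scheduled between Visits 3 and 4. The day of reduction is not given, so days 7, 14 and 21 are assumed.

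Under section 5.4.1 the delay is 3 days, whatever the day of reduction. Under section 2.2.6, for a subject whose symptoms have gone, delay = Visit 4 day − reduction day:

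- Day 7: 25 − 7 = 18 to 35 − 7 = 28 days.
- Day 14: 25 − 14 = 11 to 35 − 14 = 21 days.
- Day 21: 25 − 21 = 4 to 35 − 21 = 14 days.
- Day 7 with the full window (Visit 4 on day 18 to 42): 18 − 7 = 11 to 42 − 7 = 35 days.

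These are times without a required reading. They do not measure harm, and they assume that no new symptoms prompt another interim visit.

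**How likely the trigger is**

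- Section 5.1.1 states that 60 to 120 mg daily, this trial's range, does not produce levels above 3%. It also reports none above 3% in 80 phase I volunteers at doses under 75 mg.
- Section 2.2.2 describes a 10-week oral study of 40 or 80 mg twice daily, doubled for one more week. Methemoglobin changes never exceeded 3% there. The highest daily dose was 2 × 160 = 320 mg, or 320 / 120 = 2.7 times this trial's maximum.
- Section 5.1.1 does report "asymptomatic increases of methemoglobin levels above 5" percent, but in a 48-hour infusion study at about 8 times this trial's daily dose.

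The documents give no rate of levels above 5% at this dose, so no expected count is offered.

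**The case against.** The strongest reply is that this is loose drafting around a remote event. Section 5.4.1 refers back to section 2.2.6 and can be read as a summary of it. Taking the 3-day reading satisfies both texts, since section 2.2.6 does not forbid it. The affected subjects have already had their dose halved and their symptoms have gone. Weekly calls continue (section 2.2.4), and subjects are told to report symptoms promptly. The 5% limit is itself cautious: section 5.1.1 treats levels below 15% as below clinical toxicity.

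Most of this stands, and it sets the weight of the point. It does not remove the discrepancy. If section 5.4.1 is a summary, it dropped a condition, and one text still needs correcting. Calls about symptoms do not measure a level.

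A reader might infer three stronger claims that the documents do not support.

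- **That weeks of dosing without a reading mean a growing hazard.** Section 2.2.2 gives a nitrite half-life of about 40 minutes and a return to baseline between 3 and 6 hours. Doses are about 6 hours apart, so plasma nitrite should not build up.
- **That a first reading above 5% at Visit 4 would go unmanaged.** It is true that no numeric action is written for it, because both reduction rules are tied to interim visits. But section 2.2.4 provides for individual evaluation of concerns, section 5.4.4 has the investigator review safety data as they arise, and methemoglobin is read again at Visit 5. For subjects already reduced, the discontinuation rule in section 5.4.1 applies at Visit 4 too. What is missing is detail.
- **That subjects who start on 20 mg should be discontinued automatically on one reading above 5%.** Section 2.2.6 leaves their withdrawal to the physician. That is a legitimate choice, and a fixed rule could cost the on-drug biopsy at Visit 5.

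**Conclusion.** The point holds as a minor safety-wording correction. After a reduction for methemoglobin above 5%, section 2.2.6 makes the 3-day repeat conditional on persisting symptoms and section 5.4.1 does not. For a subject whose symptoms have gone, the next required reading moves from 3 days to Visit 4, or 18 to 28 days if the reduction is on day 7 and less if it is later.

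This rests on the plain wording of both sections, on assumed reduction days, on Visit 4 falling on day 25 to 35, and on no new symptoms in between. The reported experience at comparable daily doses makes the event very unlikely. No endpoint, analysis or power figure changes.

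**What to change.** Amend the methemoglobin paragraph of section 2.2.6 to match section 5.4.1. Suggested wording: after a reduction to 20 mg three times daily for methemoglobin above 5%, methemoglobin is repeated by finger probe at 3 days in every subject, whether or not symptoms have resolved, and the subject is discontinued if the level is still above 5%.

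Optionally, state that the same reduce-and-recheck rule applies to a first reading above 5% at Visit 4 in a subject on 40 mg three times daily. Visit 5 can serve as the recheck if it falls on day 3 after Visit 4; otherwise a brief extra check is needed. Leave subjects who started on 20 mg to physician judgment, as section 2.2.6 now does.

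The cost is a wording change and an occasional extra finger-probe visit. Section 5.4.1 already requires the unconditional repeat, and halving the dose needs no new supply, since it means one 20 mg capsule instead of two (section 2.2.1).

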2.3 STUDY ASSESSMENT

The complete study assessment and procedures are outlined in Table 1.

2.3.1. Study Visits and Procedures

Visit 1 (Screening)

The outpatient screening will take place in either the Montefiore Clinical and Translational Research Center (CTRC) or the Endocrinology Metabolism Research Center (EMRC) at the UPMC Montefiore Hospital and will last approximately 2-3 hours.

- Obtain written informed consent
- Complete history and physical examination to include body weight and height
- Medical history obtained prior to visit will be reviewed with subject. Subjects will be asked questions about any heart disease and related diseases in first degree relatives; no identifying information will be obtained. [name] will review risk factors for hypotension in subjects who are 70 to less than 80 years of age at the physical exam, in preparation for dose selection. Subjects will be asked while they are in the study to report promptly any changes in their health or medications so that the PI can evaluate any implications with study drug or participation.
- Hemoglobin and hematocrit to assess for anemia
- Blood pressure and other vital signs (temperature, pulse oximetry, breathing rate, heart rate) Blood pressure may be re-measured multiple times if out of inclusion range. This is to allow for influences of medication activation, subject nervousness, lack of fluid intake, and known factors which contribute to clinical variation.
- Transthoracic Echocardiogram (performed by trained study staff) - results of echo will confirm group placement. If subjects have had an echocardiogram within 4 weeks of the consent date, the records will be obtained prior to visit 1 and the test will be reviewed and interpreted by a study physician. Trained study staff doing echos will consist of cardiologists doing advanced echo training at UPMC under the supervision of [name]. Drs. [name], Simon and [name] are responsible for all echocardiography procedures and interpretations. The subject may be transported to a lab in the UPMC Presbyterian/Montefiore system for the echocardiogram.

Screening evaluations will include a hemoglobin and hematocrit by the Presbyterian Hospital clinical automated testing lab and are to be covered by research funds. The total volume of blood drawn is approximately 1 teaspoon (4 mL). If laboratory results exclude low hemoglobin (<11.0 g/dL males, <10.0 females) the subject will be called to arrange the baseline assessments.

Subjects who fail to meet applicable inclusion/exclusion criteria based upon the results of the screening assessment will be excluded from further study participation.

An important component of the protocol is the muscle biopsy. Subjects who refuse the first biopsy will be excluded at screening. Participants who undergo the first biopsy at Visit 3 may refuse a second pass. (Participants may also refuse a second biopsy pass at Visit 5). However, participants who refuse to complete a second biopsy at Visit 5 (prior to starting sodium nitrite) will be withdrawn from the study. Alternatively, patients who refuse the 2nd biopsy after they have completed the 4 weeks of nitrite therapy will still be included.

Visit 2 (First Baseline Assessment Visit)

Subjects will be scheduled for an outpatient EMRC and Pepper SMART Center visit within 4 weeks of screening. The subject will be asked to refrain from caffeine the morning of this visit and to limit breakfast to a lighter meal prior to coming in. The visit will last approximately 3 hours.

Interval history and brief physical exam: temperature, blood pressure, pulse oximetry, breathing rate, heart rate and body weight

Physical Function Battery:

- Cardiopulmonary Stress Exercise Testing: Exercise testing in association with air-gas-exchange, an optimal gauge of aerobic capacity will be conducted by trained research exercise

physiologists. [name] or another physician will be immediately available if needed. A computerized cycle ergometer using a ramp protocol will be used to generate a symptom limited exercise stimulus. A lightweight disposable pneumotach device face mask will be positioned over the subject's mouth and nose during the exercise for gas exchange assessments of VO_2 , VE/VCO_2 slope, and respiratory exchange ratio (RER) will be measured as well as hemodynamics (max heart rate [HR] and blood pressure [BP]), time, and ECG waveforms). Any unexpected abnormalities will be reported to a patient's cardiologist or primary care physician; continued participation in the study will require physician clearance. Both the Borg Rate of Perceived Exertion (RPE) and the Modified Borg Scale for Perceived Dyspnea (Shortness of Breath) will be completed during the CPX. The EMRC has performed similar tests in more than 1,000 volunteers ranging from elderly women in their 80's to highly trained athletes.

- Short Physical Performance Battery (SPPB): a brief performance battery is used to assess how well older persons perform simple movements that represent the building blocks of daily activities that require good lower extremity function. It is based on timed 4 meter walk, repeated chair stands, and a set of balance tests.
- Fatigability will be assessed based on rate of perceived exertion (RPE 6-20 scale) reported after a steady state walking on a treadmill. Patients will walk 1.5 miles/hour (0.67 m/sec) for 5 minutes on a treadmill as per techniques validated by Simonsick, et al. (J Am Geriatr Soc. 2014;62:347-51). Those with RPE ≥ 10 will be categorized as highly fatigued. Our prior work in HF patients indicates this steady state walking provocation is feasible for the patients we anticipate we will enroll, and that it will (appropriately) generate a wide range of perceived fatigability responses for meaningful analyses of underlying mechanisms. Aerobic capacity will be assessed with gas-exchange (as noted above) during the steady state walk for VO_2 , VE/VCO_2 slope, and respiratory exchange ratio (RER).
- Hand Grip Strength Assessment will be performed to measure muscle strength. Participants will be asked to sit in a chair without arms and squeeze a device as hard as they can with one hand at a time, rest and switch to the other hand.
- The Kansas City Cardiomyopathy Questionnaire will be used to measure disease-specific health-related quality of life (QOL). This 23-item instrument produces the following scores: Physical Limitation, Symptoms, Symptom Stability, Social Limitation, Self-efficacy, Quality of Life, and two summary measures, and is widely used as a standard by which quality of life, self-efficacy, and other personal perspectives related to functional capacity at baseline and over time. Subjects in the healthy elderly control group without HF will be asked to complete the SF-12 which is a practical, reliable and valid measure of physical health.
- 24-hour dietary recall. The study coordinator will collect a 24-recall of all foods eaten the day before from subjects for analysis for calories, macronutrients, sodium, nitrates and nitrites.

Visit 3 (Second Baseline Assessment Visit)

This visit involves a percutaneous muscle biopsy, blood draw, first dose of study medication and dispensing of study medication. To prevent acute effects of exercise on muscle mitochondria function, this fasting visit will occur 2-7 days after Visit 2. This visit will take place at the MUH-CTRC and will last 4-5 hours. Subjects will be asked to observe 8 hours fasting prior to arrival. Upon arrival subjects will be weighed and then served a standardized breakfast [15% of 30 calories/kg current body weight (CBW) and 15% of 1.0 gm protein/kg CBW, low nitrite/nitrate] in

the CTRC. A dietitian will review and adjust subjects' food choices as needed to meet the standardized diet prescription.

Interval history and brief physical exam: temperature, blood pressure, pulse oximetry, breathing rate, heart rate and body weight. Blood pressures may be re-measured to allow for clinical variation. Prior to the biopsy, study staff will call indicated subjects to hold their anti-platelet and anti-coagulation medications for 1-5 days (depending on the different medications and relative half-lives). In each instance a subject is on an anti-platelet or anti-coagulation medication, the plan to hold the medication prior to the biopsy will first be cleared by the study physician with the subject's own primary care provider or cardiologist. Physician orders for CTRC will include confirmation with subject upon arrival.

- Blood sampling via IV line to include: research blood for inflammatory peptides (IL-1, IL-6, IL-15, TNF α), platelet sample and nitrite levels. Blood samples will be drawn into a 1) heparinized syringe (baseline and approximately 30 mins. and 2 hours post study drug administration) and 2) a cell preparation tube (CPT) (baseline and approximately 30 mins and 2 hours post study drug administration). Heparinized blood will be immediately centrifuged at bedside to separate plasma and the plasma and red cells separately flash frozen for later nitrite measurements (via reductive chemiluminescence to determine that nitrite levels were increased in the muscle as described. The second tube of blood (CPT tube) will be immediately subjected to differential centrifugation in order to isolate platelets. Platelets will then be subjected to Seahorse extracellular flux analysis in order to measure bioenergetic profile including basal, non-ATP producing, maximal and non-mitochondrial respiratory rates along with glycolytic rate. Extra aliquots will be stored for use in future studies. Two 10 ml purple top and 2 10 ml red top tubes will be used to collect blood for inflammatory peptides. Total volume of blood drawn will be 88 ml (6 tablespoons).

- Skeletal Muscle Biopsies: Patients will lie comfortably in the supine position for biopsy of the vastus lateralis muscle of the non-dominant leg. Biopsy sites will be prepped with betadine. 2% xylocaine (without epinephrine) will then be administered, superficially initially and then more deeply into the muscle, using a small gauge needle. Subjects who have report a history of poor pain control or low threshold will be offered the use of a topical anesthetic cream prior to the xylocaine. Ultrasound may be used to enhance visualization of the site for the needle insertion. A small superficial incision will next be completed using a #11 blade scalpel. A 5 mm Bergstrom muscle biopsy needle will be inserted through the skin incision and advanced into the muscle. Suction will be generated using a syringe attached to the outside portion of the needle, to thereby suck skeletal muscle into a hole on the side of the needle positioned in the muscle tissue; this draws a small piece of muscle tissue (about 150 mg of muscle tissue) into the hollow shaft of the needle, which is then cut with a cutting trochar that slides through the shaft to cut the tissue drawn within its core. After harvesting the first sample, the needle will be rotated 90 degrees, and a second sample extracted to maximize yield for analysis. Additional passes of the needle may be necessary for an adequate muscle sample. The wound site will be closed with steri-strips and a sterile pressure bandage. Muscle specimens will be immediately processed, and stored. One fragment will be placed in sterile cryotubes containing RNA preservation solution (RNAlater) and immediately frozen in liquid nitrogen for measurement of mRNA expression. A second fragment will have the muscle fibers aligned for microscopy, placed in OCT, then cooled in a thawing isopentane slurry and placed in a cryotube and frozen in liquid nitrogen for morphological analysis. One specimen will immediately be used for high resolution respirometry. Briefly, muscle fibers will be dissected and immediately placed in an Oroboros respirometry. Basal respiratory rate will be measured followed by respiration after the administration of oligomycin A to assess non-productive respiration and FCCP to measure maximal respiratory capacity. A separate muscle specimen will be saved for Western blots and to measure nitrite concentrations by reductive chemiluminescence.

Subjects will rest for approximately 30 minutes post biopsy while wound is dressed and prior to baseline vitals prior to dosing. Study staff will record a baseline level of symptoms, including shortness of breath, dizziness, lightheadedness for use during weekly phone calls, prior to dosing.

Following biopsy, subjects will receive their first dose of study drug as follows:

- 14N sodium nitrite, 20 or 40 mg per physician order
- Blood pressure (sitting and then standing after 3 minutes), HR, RR, pulse oximeter and methemoglobin will be measured to ensure they are at a steady state before taking the study drug (baseline) and then approximately every 15 minutes for the 2 hours post-drug administration. Any perturbations of concern will be addressed per the Dose Reduction protocol described in Section 2.2.6.
- AE assessment
- Provide a 42-day supply of study drug, pre-filled in 4 weekly pill boxes and an extra bottle and drug diary cards to assist with compliance and reduce burden or confusion. Study staff will review medication administration and use of the drug diary card with all subjects. Study staff or CTCR RN will review biopsy site care with subjects and if indicated, remind subjects to resume their normal anti-coagulation and anti-platelet medications the following day (as indicated).
- 24-hour dietary recall. The study coordinator will collect a second 24-recall of all foods eaten from subjects for analysis for calories, macronutrients, sodium, nitrates and nitrites.

Subjects will be reminded before departure to report promptly any changes in their medication, health or symptoms of concern, not to wait for the weekly call.

Visit 4 (First Completion Assessment visit to be scheduled 25-35±7 days following first dosing of 20-40 mg oral nitrite) Subjects who need more than 42 days' supply of drug due to scheduling later in window will be issued additional at visit 3.

This visit will take place in the EMRC and/or Pepper SMART Center and is identical to visit 2 (approximately 3 hours):

Interval history and brief physical exam: temperature, blood pressure, pulse oximetry for methemoglobin %, breathing rate, heart rate and body weight; additionally, AE and symptom assessment will be collected and medication compliance via drug diary cards and pill boxes will be assessed.

Physical Function Battery:

- Cardiopulmonary Stress Exercise Testing: Exercise testing in association with air-gas-exchange, an optimal gauge of aerobic capacity will be conducted by trained research exercise physiologists. [name] or another physician will be immediately available if needed. A computerized cycle ergometer using a ramp protocol will be used to generate a symptom limited exercise stimulus. A lightweight disposable pneumotach device face mask will be positioned over a subject's mouth and nose during the exercise for gas exchange assessments VO_2 , VE/VCO_2 slope, and respiratory exchange ratio (RER) will be measured as well as hemodynamics (max heart rate [HR] and blood pressure [BP]), time, and ECG waveforms). Any unexpected abnormalities will be reported to a patient's cardiologist or primary care physician; continued participation in the study will require physician clearance. Both the Borg Rate of Perceived Exertion (RPE) and the Modified Borg Scale for Perceived Dyspnea (Shortness of Breath) will be completed during the CPX. The EMRC has performed similar tests in more than 1,000 volunteers ranging from elderly women in their 80's to highly trained athletes.

- Short Physical Performance Battery (SPPB): a brief performance battery is used to assess how well older persons perform simple movements that represent the building blocks of daily activities that require good lower extremity function. It is based on a timed 4 meter walk, repeated chair stands, and a set of balance tests.
- Fatigability will be assessed based on rate of perceived exertion (RPE 6-20 scale) reported after a steady state walking on a treadmill. Patients will walk 1.5 miles/hour (0.67 m/sec) for 5 minutes on a treadmill as per techniques validated by Simonsick, et al. (J Am Geriatr Soc. 2014;62:347-51). Those with RPE ≥ 10 will be categorized as highly fatigued. Our prior work in HF patients indicates this steady state walking provocation is feasible for the patients we anticipate we will enroll, and that it will (appropriately) generate a wide range of perceived fatigability responses for meaningful analyses of underlying mechanisms.
- Hand Grip Strength Assessment will be performed to measure muscle strength. Participants will be asked to sit in a chair without arms and squeeze a device as hard as they can with one hand at a time, rest and switch to the other hand.
- The Kansas City Cardiomyopathy Questionnaire will be used to measure disease-specific health-related quality of life (QOL). This 24-item instrument produces the following scores: Physical Limitation, Symptoms, Symptom Stability, Social Limitation, Self-efficacy, Quality of Life, and two summary measures, and is widely used as a standard by which quality of life, self-efficacy, and other personal perspectives related to functional capacity at baseline and over time. Subjects in the healthy elderly control group will be asked to complete the SF-12.
- 24-hour Dietary recall. The study coordinator will collect a post 24-hour recall of all foods eaten from subjects for analysis for calories, macronutrients, sodium, nitrates and nitrites.

Visit 5 (Final Completion Visit - 2-7 \pm 7 days following Visit 4)

Subjects will be fasting and take their last dose of study drug at home on their usual schedule prior to scheduled testing time. Upon arrival to the CTRC, subjects will be served a standardized breakfast as described in visit 3, then interval history and brief physical exam; temperature, blood pressure, pulse oximetry for methemoglobin %, breathing rate, heart rate and body weight will be documented; additionally, AE and symptom assessment, medication compliance via drug diary cards and pill boxes, and confirmation of last dose will be performed prior to assessment procedures. Prior to the biopsy, study staff will call indicated subjects to hold their anti-platelet and anti-coagulation medications for 1-5 days (depending on the different medications and relative half-lives). This visit will last approximately 2 hours.

- Blood draw to include: research blood for inflammatory peptides (IL-1, IL-6, IL-15, TNF α), platelet sample and nitrite levels: Two blood samples will be drawn into a 1) heparinized syringe and 2) a cell preparation tube (CPT). Heparinized blood will be immediately centrifuged at bedside to separate plasma and the plasma and red cells separately flash frozen for later nitrite measurements (via reductive chemiluminescence to determine that nitrite levels were increased in the muscle as described). The second tube of blood (CPT tube) will be immediately subjected to differential centrifugation in order to isolate platelets. Platelets will then be subjected to Seahorse extracellular flux analysis in order to measure bioenergetic profile including basal, non-ATP producing, maximal and non-mitochondrial respiratory rates along with glycolytic rate. Extra aliquots will be stored for use in future studies. Total volume of blood drawn will be 56 ml (4 tablespoons)

